**SECTION FIVE: SAMPLE SIZE JUSTIFICATION**

Our estimated sample size is 224 patients (240, assuming a 10% attrition rate): 112/group, yielding 80% power to detect a 0.5% difference in the pre-post change in HbA1c (two-tailed t-test with  $\alpha = .05$ ) over 6 months. Our power calculation is based on Polisena et al.'s meta-analysis. We computed a sample size-weighted median of the 12 standard deviations (SD) for HbA1c, yielding a value of 1.2%. If the SD of the pre-post 6-month change in HbA1c is 1.2% in each group, a 0.45% difference in this 6-month change yields a 0.42 effect size (ES). This ES is realistic, falling between 2 sets of reductions in the literature: the Diabetes Control and Complications Trial (1% decline in HbA1c reduced microvascular complications by 30%) and RCTs/meta-analyses citing reductions of 0.3% as "clinically significant". Our reduction of 0.45% falls between those limits, is clinically significant/meaningful, as patients can see improvements in their scores. In a systematic review of 13 RCTs (n=4,207) telehealth was associated with a clinically significant mean HbA1c decline of -0.44% compared to COM. In medically underserved patients, telehealth led to a net improvement in HbA1c, cholesterol, and BP. Although our main power calculation refers to our primary outcome (HbA1c), power is still acceptably high for secondary variables (SE, distress or QoL) such that 112 patients/group will yield 80% power to detect an effect size of 0.4 SDs, using a simple t-test to sample size and power.

Figure 4. Study Plan: Following 240 Patients for 12 Months Randomized to Either DTM (n=100) or COM (n=100) with 6 Month Intervention, Assuming 10% Attrition, Resulting in a Final Sample Size of 200

Year	2019												2020												2021												2022																																																	
Month	1	2	3	4	5	6	7	8	9	10	11	12	13	14	15	16	17	18	19	20	21	22	23	24	25	26	27	28	29	30	31	32	33	34	35	36	37	38	39	40	41	42																																												
Enrollment	CAB Focus Group: Confirm Outcomes, Preliminary Intervention Adaptions & Study Design												PAC Focus Group: Confirm Outcomes, Preliminary Intervention & Study Design Adaptions & Recommendations												Provider Focus Group: Pre-Pilot Adaptation Recommendations												CAB: PAC: Provider Focus Group Analysis												Pre-Pilot Adaptation Approval by the CAB																																					
	Pilot												Pilot Patient/Caregiver Focus Groups (2)												Pilot Analysis												PAC Focus Group: Post-Pilot Adaptions												Provider Focus Group: Post-Pilot Adaptions												CAB Finalizes Intervention Adaption												Analysis													
Interventions	CAB												PAC												CAB												Pilot Study												Pilot Focus Groups												PAC												CAB												CAB/BPAC	
	6 MONTH FOLLOW UP												12 MONTH FOLLOW UP												12												12												12												12												12													
Study Aims	Specific Aim 1: Assess usability of an evidence-based DTM intervention utilizing a community based participatory research approach and adapt it to facilitate acceptability and feasibility in a population of Hispanic/Latino patients with T2D, and their caregivers and providers.																																										Specific Aim 2: Assess whether Hispanic/Latino patients receiving DTM attain significantly improved patient-centered outcomes compared to COM, through a CER RCT. Expected outcomes include: improved diabetes quality of life, glycemic management, blood pressure, cholesterol, medication adherence, and diabetes self-efficacy, and reduced diabetes distress, problem areas in diabetes, inpatient utilization, unscheduled T2D physician visits and sick days.																																											

1. Estimated number of potentially eligible participants (describe how number was determined [e.g., Electronic Health Record, claims data, clinic logs, administrative data, other]):	4092
2. Total number of study participants expected to be screened:	400
3. Total number of study participants expected to be eligible of those screened:	400
4. Target sample size (use same number stated in milestones):	200
5. If applicable, total number of practices or centers that will enroll participants:	2
6. Projected month first participant enrolled (month after project initiation):	1/2019
7. Projected month last participant enrolled (month after project initiation):	12/2021
8. Projected rate of enrollment (anticipated number enrolled per month of enrollment period):	8 to 10
9. Estimated percentage of participant dropout:	10%

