**5. RESOURCES AVAILABLE TO CONDUCT THE HUMAN RESEARCH**

- *Explain the feasibility of meeting recruitment goals of this project and demonstrate a potential for recruiting the required number of suitable subjects within the agreed recruitment period*
  - *How many potential subjects do you have access to?*
- *Describe your process to ensure that all persons assisting with the trial are adequately informed about the protocol and their trial related duties and functions*

The specific population affected by the research is underserved T2D patients. Our estimated sample size is 200 patients (240, assuming a 10% attrition rate). We propose to study H/L patients with T2D, recruited from the Ambulatory Care Unit at LIJMC and the Division of General Internal Medicine Practice located in Queens NY, one of the most diverse populations in the world. We also propose to recruit at Southside Hospital. NUMC and Glen Cove Hospital as well as the Dolan Family

Health Center. We selected these sites because 1) clinic patient statistics meet our enrollment criteria, with 4,092 adults H/L patients with T2D (well over the 200 recruitment number required). 2) clinicians at these sites express enthusiasm for/commitment to the study and what it might mean for their H/L patients with T2D. These sites provide a real-world setting for implementation because LIJMC is where our target population of H/L disparity patients with T2D (many with limited English proficiency) receive their care (H/Ls comprise 27.5% of Queens' population).

Staff have all reviewed and been trained on methods for the study outlined in the protocol. There will be an initial kick off meeting to discuss the protocol in further detail. They have all completed CITI training and compliance for HIPPA data. |

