### INCLUSION AND EXCLUSION CRITERIA

**Inclusion criteria:** 1) H/L patients with a diagnosis of T2D alone or in combination with other chronic conditions (e.g., heart disease); 2) age > 18 speak English or Spanish.

Caregivers age >18 taking care of a patient with T2D alone or in combination with other chronic conditions.

Providers who treat patients with T2D alone or in a combination with other chronic conditions

**Exclusion criteria:** 1) patient is not a H/L with a diagnosis of T2D; 2) age <18.  
Identification of study participants: There are 4,092 H/L patients with T2D fitting our inclusion criteria.  
Caregivers age <18 who do not take care of a patient with T2D or in combination with other chronic conditions  
Providers who do not treat patients with T2D alone or in a combination with other chronic conditions.

Our goal is to enroll 224 (240, assuming a 10% attrition rate) patients/20-months. With a 50% acceptance rate (estimated on our previous enrollment experience), we will need to approach 400 total patients (or 20/month) to enroll 12 patients per month, easily reaching our goal of 224 participants over the 20-month accrual period.

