## 8. NUMBER OF SUBJECTS

- *Indicate the total number of subjects to be accrued locally. If applicable, distinguish between the number of subjects who are expected to be pre-screened, enrolled (consent obtained), randomized and complete the research procedures.*
- *If your study includes different cohorts, include the total number of subjects in each cohort.*
- *If this is multisite study, include total number of subjects across all sites.*

For the pilot test in Aim 1, we will have 12 subjects. For the RCT in Aim 2, we will randomize 224 patients. We plan to consent 224 patients assuming there will be a 10% attrition rate.

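### The sample-size statement joins two calculations (0.45% with an effect size of 0.42, 80% power for 0.5%), and the trial size is variously 200, 224 and 240

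*Combined protocol and SAP*

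**What the plan says.** Section Five (Sample Size Justification) opens with "Our estimated sample size is 224 patients (240, assuming a 10% attrition rate): 112/group, yielding 80% power to detect a 0.5% difference". The outcome there is HbA1c change over 6 months, and the test is a two-sided t-test at alpha 0.05. It takes an SD of the change of 1.2% in each group, states that "a 0.45% difference in this 6-month change yields a 0.42 effect size (ES", and argues for clinical relevance on the smaller figure: "Our reduction of 0.45% falls between those limits". For secondary outcomes it says that "112 patients/group will yield 80% power to detect an effect size of 0.4 SDs".

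The trial size differs by place:

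- Section 5: "Our estimated sample size is 200 patients (240, assuming a 10% attrition rate".
- Section 7 and Section Five: 224, or 240 with 10% attrition.
- Section 8: "For the RCT in Aim 2, we will randomize 224 patients". Its next sentence gives 224 as the number consented with 10% attrition already assumed.
- Section 12, 1bi and 1bii: 200 randomised (240 with attrition), with a maximum of 100 per arm.
- Section 12, tertiary analyses: 100 per group.
- Figure 4 caption: 240 patients followed, "Randomized to Either DTM (n=100) or COM (n=100) with 6 Month Intervention, Assuming 10% Attrition, Resulting in a Final Sample Size of 200".
- Enrolment table after Figure 4: target 200, dropout 10%, 8 to 10 enrolled per month.

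On recruitment, section 6 draws 400 patients at random, and section 7 assumes 50% acceptance and says "we will need to approach 400 total patients (or 20/month) to enroll 12 patients per month" over 20 months.

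**The concern.** HbA1c change is the primary outcome and the stated basis of the sample size, so the difference, SD, effect size, power and N in this paragraph should form one consistent set. They do not. The headline difference and the effect size come from one calculation; the group size and the clinical argument come from another. In addition, 224 is the number before the attrition allowance in Section Five and the number with attrition included in section 8.

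At stake are the power for the effect that the protocol defends, the number of patients the ethics board is asked to approve, and the planned sample size that the promised CONSORT report must state and justify.

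**Working it through.** **Inputs, from Section Five:** SD of change 1.2% per group, two-sided two-sample t-test, alpha 0.05, equal groups. Attrition 10% and acceptance 50% are the protocol's own figures. Power is from the noncentral t distribution with 2n − 2 degrees of freedom and noncentrality (difference/SD) × √(n/2).

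**1. What reproduces.** By the normal approximation, n per group = 2 × (1.960 + 0.842)² × SD² / difference². For 0.45% this is 2 × 7.849 × 1.44 / 0.2025 = 111.6, so 112 per group (113 by the t-test). So 112 per group with 80% power is the calculation for 0.45%.

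**2. Effect size.** 0.45/1.2 = 0.375; 0.5/1.2 = 0.417. To get 0.42 from 0.45%, the SD would have to be 0.45/0.42 = 1.07%, which appears nowhere.

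**3. Power by number evaluable per group.**

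| Per group | 0.45% (0.375 SD) | 0.48% (0.40 SD) | 0.5% (0.417 SD) |
|---|---|---|---|
| 90 | 70.6% | 76.1% | 79.4% |
| 100 | 75.1% | 80.4% | 83.5% |
| 101 | 75.6% | 80.8% | 83.8% |
| 108 | 78.3% | 83.3% | 86.2% |
| 112 | 79.8% | 84.6% | 87.4% |

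At 112 per group the noncentrality is 0.375 × √56 = 2.81 for 0.45% and 0.417 × √56 = 3.12 for 0.5%. The stated 80% for 0.5% is therefore about 7 points too low; 80% for 0.5% needs only 92 per group. The secondary claim of 80% for 0.4 SD fits 100 per group, not 112.

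**4. Attrition.** 200/0.9 = 222.2, so 223; 224/0.9 = 248.9, so 249. Neither is 240. Conversely, 240 × 0.9 = 216. Going from 240 to 224 is a 6.7% loss (1 − 224/240), and from 240 to 200 is 16.7% (1 − 200/240).

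**5. Power after 10% loss of 6-month data.**

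- 224 randomised leaves 224 × 0.9 = 201.6, about 100 to 101 per group: 75–76% for 0.45%, about 84% for 0.5%.
- 240 randomised leaves 216, or 108 per group: 78.3% and 86.2%.
- If enrolment stopped at the 200 that the draw yields (step 6) and 10% were then lost, 180 would remain: 71% and 79%.

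**6. Recruitment.** 400 × 0.5 = 200 enrolled, not 224 or 240. Twenty approached per month × 0.5 = 10 enrolled per month, not 12. Over 20 months, 224 needs 11.2 enrolled and 22.4 approached per month, and 240 needs 12 and 24. The draw would have to be 224/0.5 = 448 or 240/0.5 = 480, which is 48 or 80 more than 400.

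**The case against.** The best defence is that the planned group size is sound. 112 per group follows from 0.45%, SD 1.2% and 80% power, so the fault lies in mismatched labels. Where the power figures are wrong, they err on the safe side: power for 0.5% exceeds 80% at 100, 108 and 112 per group, and power for 0.4 SD exceeds 80% as well. Section 8 does state a number to randomise, and reading its 224 as including attrition leaves about 100 per group. That agrees with the tertiary-analysis text, the final 200 in Figure 4 and the enrolment-table target, and the enrolment table's 8 to 10 per month is consistent with 200 over 20 months. All of this is fair, but that reading contradicts Section Five, where 112 per group carries the power statement before attrition is added. It also gives only about 75% power for the 0.45% that the text defends.

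A second argument is that the planned analysis is a mixed-model ANCOVA, and that outcomes will be collected after discontinuation and imputed where missing. Complete loss of 10% of the data is indeed an upper-end assumption. If baseline HbA1c is a covariate (the primary-analysis text does not clearly say so) and variances are equal at both times, the residual SD is 1.2 × √((1 + r)/2). An assumed baseline-to-6-month correlation r of 0.8 to 0.5 then gives 79% to 86% power for 0.45% at 100 per group. The documents give no correlation, so this gain cannot be claimed, and the protocol itself justifies N by a t-test. It would not correct the effect size or settle the N.

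Finally, 50% acceptance is an estimate, and 4,092 patients are available, so the shortfall in the draw is easily made up. The 180-evaluable case is conditional; no section plans for it.

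**Conclusion.** The concern holds. On the plan's own inputs, 0.45% is an effect size of 0.375, not 0.42, and 112 per group gives 87% power for 0.5%, not 80%. The numbers to be randomised conflict (200, 224 and 240), and 240 matches 10% attrition from neither base. On the t-test the plan names, neither 224 nor 240 randomised gives 80% power for 0.45% if 10% of patients have no 6-month data (75–76% and 78%); both exceed 80% for 0.5% (84% and 86%). Whether the trial meets its stated power thus depends on which sentence is read. The power figures assume an SD of 1.2%, an unadjusted comparison of change, and total loss of data in the 10%; less loss or a strong baseline adjustment would raise them. The effect-size error and the conflicting N depend on none of these. This must be corrected, because it is the justification for the primary analysis.

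**What to change.** 1. In Section Five, name one target difference with its effect size: 0.45% (0.375) or 0.5% (0.42).
2. State one number randomised, one number evaluable after 10% attrition, and the resulting power. The choice is the sponsor's:

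| Randomised | Evaluable | Power for 0.45% | Power for 0.5% |
|---|---|---|---|
| 224 | about 201 | 75–76% | about 84% |
| 240 | 216 | 78% | 86% |

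   For 80% power after attrition, 0.45% needs 113 evaluable per group (226/0.9 = 251.1, so 252 randomised). A target of 0.5% needs 92 per group (184/0.9 = 204.4, so 206 randomised in equal arms).
3. Correct the 0.4 SD statement to the evaluable number: 80% at 100 per group, 83% at 108, 85% at 112.
4. Use the chosen numbers in sections 5, 7 and 8, in section 12 (1bi, 1bii and the tertiary analyses), in the Figure 4 caption and in the enrolment table.
5. Size the random draw to match at 50% acceptance (448 for 224, 480 for 240) and correct the monthly rates.
6. Say whether the 100-per-arm DTM maximum in 1bii refers to patients randomised or patients remaining after attrition.

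Keeping 224 or 240 costs protocol wording and 48 to 80 more approaches from the existing list of 4,092. Aiming for 80% power at 0.45% after full 10% loss adds 12 patients to 240. If the 100-per-arm maximum means patients randomised, 112 or 120 per arm exceeds the stated DTM capacity, and that cost cannot be judged from the documents.

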### 13. SPECIMEN BANKING

- *If specimens will be banked for future research, describe where the specimens will be stored, how long they will be stored, how they will be accessed and who will have access to the specimens*
- *List the information that will be stored with each specimen, including how specimens are labeled/coded*
- *Describe the procedures to release the specimens, including: the process to request release, approvals required for release, who can obtain the specimens, and the information to be provided with the specimens.*

N/A

### 14. DATA MANAGEMENT AND CONFIDENTIALITY

- *Describe the data and specimens to be sent out or received. As applicable, describe:*
  - *What information will be included in that data or associated with the specimens?*
  - *Where and how data and specimens will be stored?*
  - *How long the data will be stored?*
  - *Who will have access to the data?*
  - *Who is responsible for receipt or transmission of data and specimens?*
- *Describe the steps that will be taken to secure the data during storage, use and transmission.*

The investigators will use IRB-approved and HIPAA-compliant measures to maintain confidentiality, privacy and data security. Data privacy and security procedures will include: a) training staff on data sensitivity and protocols for safeguarding confidentiality; b) storing and processing sensitive hardcopy in a secured, centralized location; c) securing sensitive hardcopy in locked files when not in use; d) removing names, addresses, and other direct identifiers from hardcopy and computer-readable data when they are no longer necessary for patient tracking and then using encrypted codes for subsequent identification of participants; e) destroying all identifiable linkages to data after data accuracy has been verified and final analyses have been completed; f) using restricted logon

identification and password protection computer protocols for all computerized entry, retrieval, and analysis.

RedCap and OneDrive are the only programs being used to restore research data

## 15. DATA AND SAFETY MONITORING PLAN

*A specific data and safety monitoring plan is only required for greater than minimal risk research. For guidance on creating this plan, please see the [Guidance Document](#) on the HRPP website.*

*Part I – this part should be completed for all studies that require a DSMP.*

*Part II – This part should be completed when your study needs a Data and Safety Monitoring Board or Committee (DSMB/C) as part of your Data and Safety Monitoring Plan.*

### Part I: Elements of the Data and Safety Monitoring Plan

- Indicate who will perform the data and safety monitoring for this study.*
- Justify your choice of monitor, in terms of assessed risk to the research subject's health and well being. In studies where the monitor is independent of the study staff, indicate the individual's credentials, relationship to the PI, and rationale for selection*
- List the specific items that will be monitored for safety (e.g. adverse events, protocol compliance, etc)*
- Indicate the frequency at which accumulated safety and data information (items listed in # above) will be reviewed by the monitor (s) or the DSMB/C.*
- Where applicable, describe rules which will guide interruption or alteration of the study design.*
- Where applicable, indicate dose selection procedures that will be used to minimize toxicity.*
- Should a temporary or permanent suspension of your study occur, in addition to the IRB, indicate to whom will you report the occurrence.*

#### **Adverse Events and Data and Safety Monitoring Plan**

We do not expect any adverse events directly attributable to the intervention. Although discussions with our IRB indicate that the risk proposed by this intervention does not meet the requirements for establishing a Data Safety Monitoring Board (DSMB), we nonetheless will establish a DSMB to review aggregate data on a bi annually basis to review possible safety issues. Any adverse events will be reported immediately to the IRB.

### Part II: Data and Safety Monitoring Board or Committee

- When appropriate, attach a description of the DSMB.*
- Provide the number of members and area of professional expertise.*
- Provide confirmation that the members of the board are all independent of the study.*

--

## 16. WITHDRAWAL OF SUBJECTS

- *Describe anticipated circumstances under which subjects will be withdrawn from the research without their consent*
- *Describe procedures for orderly termination*
- *Describe procedures that will be followed when subjects withdraw from the research, including partial withdrawal from procedures with continued data collection.*

The patients and CAB members in the focus group or structured interviews may withdraw from the study at any time after giving consent. The study may discontinue at any time. Any actions that may follow such discontinuation of the study will have no impact upon patient care or employment.
--

## 17. RISKS TO SUBJECTS

- *Describe any potential risks and discomforts to the subject (physical, psychological, social, legal, or other) and assess their likelihood and seriousness and whether side effects are reversible. Where appropriate, describe alternative treatments and procedures that might be advantageous to the subjects.*
- *Include risks to others , like sexual partners (if appropriate)*
- *Discuss why the risks to subjects are reasonable in relation to the anticipated benefits and in relation to the importance of the knowledge that may reasonably be expected to results*
- *Describe the procedures for protecting against or minimizing any potential risks, including risks to confidentiality, and assess their likely effectiveness.*

We do not anticipate any significant physical, psychological, or social risk to the study patients. All risks and benefits of participation will be explained to participants and included in the written consent forms. Participants will be at minimal risk and will be informed of their right to withdraw from the study at any time. All identifiable information will be maintained with strict confidentiality measures by the investigators.
--

## 18. RESEARCH RELATED HARM/INJURY

- *Describe the availability of medical or psychological resources that subjects might need as a result of anticipated problems that may be known to be associated with the research.*
- *If the research is greater than minimal risk, explain any medical treatments that are available if research-related injury occurs, who will provide it, what will be provided, and who will pay for it.*

We do not anticipate any significant physical, psychological, or social risk to the study patients. All risks and benefits of participation will be explained to participants and included in the written consent forms. Participants will be at minimal risk and will be informed of their right to withdraw from the study at any time. All identifiable information will be maintained with strict confidentiality measures by the investigators.

